1.0 Study Summary

Study Title	The role of altered nutrient partitioning in food reward
Study Design	This is a within-subjects crossover study design that involves a conditioning paradigm in which participants are exposed to novel flavored beverages paired with sugars and non-nutritional sweeteners, and assessment of energy expenditure and blood metabolites will be performed during the conditioning paradigm. A subset of participants will undergo fMRI measurements and metabolic chamber measurements.
Primary Objective	To assess the feasibility of measuring reward response following a flavor-nutrient conditioning paradigm across the normal to obese body mass index range and in states of altered metabolic health
Secondary Objective(s)	To develop an appropriate protocol for measuring metabolic flexibility in a "flex" metabolic chamber
Study Population	The general US population
Sample Size	15
Research Intervention(s)/ Investigational Agent(s)	Blood measurements, resting and postprandial energy expenditure and substrate oxidation, questionnaires, magnetic resonance imaging
Study Duration for Individual Participants	6-7 weeks in total: Week 1: Training Session (1 hour) Weeks 2-4: Behavior Sessions (4 sessions x 2.5 hours each) Week 5: Post-testing Session with fMRI (only a subset of participants; 3 hours) Week 5: Post-testing Session without fMRI (a majority of participants; 1 hour) Weeks 6-7: Metabolic chamber sessions (2 sessions x 6 hours each, with 5-day washout between sessions) 4 days total of controlled feeding with food provided by the metabolic kitchen
Acronyms and Definitions	REE: resting energy expenditure; MRI: magnetic resonance imaging; FBRI: Fralin Biomedical Research Institute; CHBR: Center for Health Behavior Research

2.0 Objectives

2.1 *Describe the purpose, specific aims, or objectives of this study:*

PROTOCOL (STUDY) TITLE AND NUMBER

The first aim of this study is to assess the feasibility of measuring reward response following a flavor-nutrient conditioning paradigm across the normal to obese body mass index range and in states of altered metabolic health. The second aim is to develop a protocol for measuring metabolic flexibility in a "flex" metabolic chamber over a 6-hour measurement.

2.2 State the hypotheses to be tested:

We hypothesize that reinforcement learning will be impaired with increasing obesity and that metabolic flexibility can be determined utilizing data produced from a 6-hour measurement inside a "flex" metabolic chamber.

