Indirect calorimetry is a powerful tool for determining energy expenditure and macronutrient oxidation in response to a mixed-macronutrient diet or meal. In other words, it allows for a versatility in measurement of metabolic flexibility to both fat and carbohydrate in a physiologically relevant manner. Indeed, a new method for assessing metabolic flexibility to a high-carbohydrate or high-fat meal using indirect calorimetry in a large, whole-room metabolic chamber has recently been published (McDougal et al. 2020); however, the reproducibility of this method across metabolic chambers and clinical populations has not yet been determined. Furthermore, this methodology is designed around use of a 27 m³ chamber, which requires a relatively long duration of measurement for an appropriate temporal resolution of measured O₂ and CO₂ concentrations to determine energy expenditure and macronutrient oxidation (Chen et al. 2018). The Fralin Biomedical Research Institute houses two state-of-the-art metabolic chambers. The smaller of the two chambers, approximately 4.6 cubic meters, allows for more rapid and accurate measurement of O₂ and CO₂ compared to large chambers and is specifically designed for conducting dynamic metabolic studies over shorter measurement durations. This smaller “flex” chamber is one of only a few in the world, and as such, no methodologies to assess metabolic flexibility specifically in the “flex” chamber have been developed. Thus, we are poised to take advantage of novel technology to lead the development of a new method to assess a key component of metabolic health.

3.2 Describe any relevant preliminary data:

This is a new project without preliminary data collected.

3.3 Based on the existing literature, provide the scientific or scholarly rationale for and significance of your research and how will it add to existing knowledge:

PROTOCOL (STUDY) TITLE AND NUMBER

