5.0 Study Design and Statistical Analysis Plan

5.1 *Describe the basic study design/approach (e.g., qualitative study using five focus groups of first year students to describe assimilation into the university community; randomized controlled trial of a behavioral change intervention to increase dietary intake of whole grains; pre- post-test evaluation of new pedagogical techniques to improve adult literacy):*

This study consists of two main aims. In the first aim, a within-subjects design will be used to compare the rewarding properties of two beverages, one containing 75kcal of sugar and one containing 0 kcal sucralose in individuals with normal weight and with excess adiposity or high body mass index. In a subset of participants, neural activation to each of the beverage tastes measured by fMRI will be compared. In the second aim, a within-subjects design will be used to compare metabolic response to a high-carbohydrate and high-fat test meal using a 6-hour metabolic chamber stay.

5.2 *Describe corresponding data analysis plan/approach (e.g., content analysis of focus group transcripts; descriptive analysis followed by linear regression modeling; nonparametric analysis of pre- and post-test measures):*

The first aim will use linear mixed effects models to compare ratings of the beverages and control for confounding variables. Linear regression will be used to relate blood and energy expenditure measures to liking and other subjective ratings. Standard preprocessing and statistical techniques for fMRI data will be used to compare beverages and look for relationships between neural activity and physiological measures. The second aim will use linear mixed effects models to compare energy expenditure and substrate oxidation to the test high-carbohydrate and high-fat meals measured in the metabolic chamber. Measures of metabolic flexibility will include changes in respiratory exchange ratio in response to each meal, the time to reach peak respiratory exchange ratio after meal consumption, slope from baseline to peak respiratory exchange ratio, and rate and slope of the return to baseline respiratory exchange ratio.

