8.0 Procedures Involved

8.1 *Describe and explain the study design:*

This is a crossover design and within-subjects analysis plan where participants receive all conditions during the flavor-nutrient conditioning paradigm of Aim 1. A subset of participants will also undergo fMRI scanning for Aim 1. All participants will undergo the controlled feeding diet and metabolic chamber measurements for Aim 2.

8.2 *Provide a description of:*

- *All research procedures being performed*
- *If the study has more than one procedure, session, and/or subject population, describe each procedure, session, and/or study population separately. For complex studies, you are encouraged to include a figure or chart.*

Study Overview:

Approximately 15 people from the general population will be recruited for Aim 1 (without fMRI) and Aim 2 of this randomized crossover design study conducted at FBRI. Of these 15 people, 5 will also undergo fMRI scanning as a part of Aim 1. This will be an approximately 6- to 7-week study. Participants will report to the research laboratory in Week 1 for the consent and training session. They will return to the research laboratory to complete 2 behavior sessions per beverage and a final post-testing session in Aim 1. Participants who are asked to complete the fMRI scan will undergo this measurement during the final post-testing session. For Aim 2, participants will report to the metabolic kitchen at FBRI for 2 days preceding each chamber measurement day to collect food to be consumed for each of those days. On each metabolic chamber measurement day, they will report to the metabolic chambers located in [name]. There will be a 5-day washout period between the first metabolic chamber session and controlled feeding for the second metabolic chamber session.

Recruitment and Screening:

Approved study recruitment materials will be distributed in the follow ways. Flyers will be posted on bulletin boards and approved posting sites throughout Roanoke, Blacksburg, and surrounding areas. Digital advertisements will be displayed on [name] lab and CHBR social media, VT News, and in list serves with permission.

PROTOCOL (STUDY) TITLE AND NUMBER

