AIM 2:

Controlled Feeding:

Participants will consume a standardized diet (50% carbohydrate, 30% fat) for 2 days prior to each metabolic chamber session. Total daily energy needs for each participant will be estimated using average resting energy expenditure determined during completion of Behavior Sessions 2 and 4 in Aim 1 and an activity factor derived from the physical activity questionnaire completed as part of the Consent and Training Session in Aim 1. The 2-day diet will be developed by a registered dietitian, and all foods will be prepared and assembled in the metabolic kitchen located in [name].

Participants will report to the metabolic kitchen to pick up coolers of food. Participants will be provided with all foods and drinks, except water, for the 2 days preceding each metabolic chamber measurement and instructed to consume all foods and beverages provided in the coolers.

Metabolic Chamber Sessions:

Participants will report to the metabolic chamber lab in [name] after a >8 hour (overnight) fast. Participants will also be asked to abstain from moderate-to-vigorous physical activity for at least 24h prior to their session.

Participants will then enter the flex metabolic chamber, which is outfitted with a bed, pillows, and a TV, to rest quietly during the fasting measurement. The fasting measurement will take approximately 50 minutes. After a fasting measurement, participants will be instructed to consume a high-carbohydrate (60% carbohydrate, 20% fat) or high-fat (60% fat, 20% carbohydrate) test meal within 5 minutes. Participants will then rest inside the chamber, without sleeping, for 5 hours during the post-consumption measurement.

The metabolic chamber operates under the same indirect calorimetry assumptions and principles as the metabolic cart, but the size of the chamber (4.6 cubic meters) allows for longer measurements with better comfort for participants compared with the metabolic cart. There are no known risks associated with this method of indirect calorimetry, and participants may wear normal clothes during the procedure. The chamber is outfitted with a 2-way intercom system, and one wall is clear plastic; participants will be able to see and communicate with research personnel throughout the test. Should a participant become

PROTOCOL (STUDY) TITLE AND NUMBER

uncomfortable with the test, they may choose to stop the procedure at any time. (See picture below.)

8.3 *Describe:*

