14.0 Number of Subjects

14.1 *Indicate the total number of subjects to be enrolled and how this number was determined (e.g., sample size calculation [show], number of available subjects in a finite pool, number of tests funding award would allow):*

We plan to consent approximately 25 participants with the intent of having 15 participants complete all sessions of Aims 1 and 2, and we anticipate having 5 of those participants also complete an fMRI scan. These numbers were determined based on our pilot grant award amount, the sample size we anticipate needing to generate pilot/feasibility data, and the anticipation of ~40% either dropping out or being excluded after enrollment (e.g., unable to determine flavors equally liked and unfamiliar for the conditioning paradigm, hemoglobin A1C outside of inclusion range, scheduling challenges, etc.).

14.2 *If this is a multi-site study, indicate the number of subjects to be enrolled at this site and the total to be enrolled from all sites:*

PROTOCOL (STUDY) TITLE AND NUMBER

Single site.

14.3 If applicable, indicate the number of potential subjects you expect to screen for enrollment, and the number of subjects you will need to complete the research procedures:

We anticipate screening via the online screening survey approximately 150 potential participants. We anticipate enrolling and screening approximately 25 participants during our Consent and Training Session. We intend to have 15 participants complete all procedures except the fMRI scan. Of those 15 participants, we intend to have 5 participants complete the fMRI scan.

14.4 If the study has more than one procedure, indicate the total number of subjects to undergo each procedure separately:

Consent and Training Session (flavor tasting/rating, anthropometrics, fingerstick sample for HbA1C): 25 participants

Behavior Sessions 1 and 3 (IV catheter blood draw): 15 participants

Behavior Sessions 3 and 4 (metabolic cart): 15 participants

Post-Test Session without fMRI (flavor and beverage tasting/rating): 15 participants

Post-Test Session with fMRI (flavor and beverage tasting/rating and fMRI scan): 5 participants

Metabolic Chamber Sessions 1 and 2: 15 participants

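### The stated Aim 2 model compares meals, and the person-level flexibility indices have no repeatability analysis or criterion; the duplicate chamber fasting periods could supply the baseline part

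*Combined protocol and SAP*

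**What the plan says.** Section 2.1 sets Aim 2 as developing a protocol to measure metabolic flexibility in the flex chamber. The hypothesis in section 2.2 is that "metabolic flexibility can be determined utilizing data produced from a 6-hour measurement". No success criterion is given.

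Section 5.2 gives one model for this aim: "The second aim will use linear mixed effects models to compare energy expenditure and substrate oxidation to the test high-carbohydrate and high-fat meals". It then names indices that can be computed for each person: "Measures of metabolic flexibility will include changes in respiratory exchange ratio in response to each meal", followed by time to peak, slope up to the peak, and rate and slope of the return. No repeatability, agreement, between-person variance or threshold is attached to any of them.

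Section 8.2 (Aim 2) describes two chamber sessions. Each follows the same 2-day standardised diet, an overnight fast of more than 8 hours and 24 hours without moderate or vigorous activity. In each session, "The fasting measurement will take approximately 50 minutes"; one test meal and 5 hours of measurement follow. One session has the high-carbohydrate meal (60% carbohydrate, 20% fat) and the other the high-fat meal (60% fat, 20% carbohydrate).

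The documents differ on who enters the chamber. Section 8.1 says: "All participants will undergo the controlled feeding diet and metabolic chamber measurements for Aim 2". Section 14.4 lists: "Metabolic Chamber Sessions 1 and 2: 15 participants". The design entry in section 1.0 says: "A subset of participants will undergo fMRI measurements and metabolic chamber measurements".

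**The concern.** Two meals with carbohydrate and fat shares reversed should produce different mean substrate oxidation in almost any group. Finding that difference shows that the chamber registers what was eaten. It does not show that the chamber can tell a more flexible person from a less flexible one, and section 3.1 defines inflexibility as something that characterises people. Showing that requires the spread between people to be set against the error within a person.

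At stake is what Aim 2 can report. Under the present text, a significant meal contrast could be presented as support for the hypothesis when it does not bear on measurement in individuals. The matched fasting duplicates, which could give a first piece of the error structure of a new method, would go unused for that purpose.

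**Working it through.** **1. The plan's own figures.** Section 14.1 consents 25 people, expects about 40% loss and aims for 15 completers: 15 / (1 − 0.40) = 25, which reproduces. Chamber session length: 50 + 5 + 300 = 355 minutes, about 6 hours, which agrees with the stated duration. The documents give no alpha, effect size, SD or power.

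**2. What a significant meal contrast can show.** Write a person's meal difference as D = μ + T + e. T is the stable personal part with variance r, and e is day-to-day error with variance 1 − r, so the total SD is 1 and r is the reliability of D. The paired t statistic depends on μ relative to the total SD and on n; r does not enter. With n = 15 and an assumed two-sided alpha of 0.05, the noncentrality is μ × √15:

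| Assumed μ (in SD of D) | Power |
|---|---|
| 0.5 | 0.44 |
| 0.78 | 0.80 |
| 1.0 | 0.95 |
| 1.5 | 0.9997 |

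Simulation at μ = 1.5 (15 people, 20,000 runs for each value of r; test-retest correlation averaged over 3,000 of them):

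| True r | Share significant | Mean test-retest correlation |
|---|---|---|
| 0 | 0.99945 | 0.00 |
| 0.25 | 0.99975 | 0.24 |
| 0.5 | 0.9998 | 0.48 |
| 0.75 | 0.9998 | 0.74 |
| 0.95 | 0.9995 | 0.95 |

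The test gives the same answer whether individual responses are pure noise or almost perfectly repeatable.

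**3. What the fasting duplicates can give.** With two fasting values per person and n = 15, the within-person variance is the sum of squared differences divided by 2n, on 15 df.

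- 95% limits of the SD, as multiples of the estimate: √(15/27.49) = 0.74 and √(15/6.26) = 1.55.
- If a session effect is removed (14 df): 0.73 to 1.58.
- Observed one-way ICC of 0.8: F = (1 + 0.8)/(1 − 0.8) = 9. Lower: 9/2.89 = 3.11, so (3.11 − 1)/(3.11 + 1) = 0.51. Upper: 9 × 2.95 = 26.5, so (26.5 − 1)/(26.5 + 1) = 0.93.
- Observed ICC of 0.9: 0.74 to 0.96.
- If only 5 people entered the chamber (an assumed size for the subset in section 1.0), the SD limits widen to 0.62 to 2.45 times the estimate.

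**4. What they cannot give.** Each meal is given once per person, so no meal response is replicated. In any session-level summary, person-by-meal variation cannot be separated from day-to-day error. For RER change, error SD = fasting error SD × √(1 + k² − 2ρk), where k is the ratio of post-meal to fasting error and ρ is their correlation. Neither is in the documents. Over assumed ranges k = 1 to 2 and ρ = 0 to 0.8, the multiplier runs from √(1 + 1 − 1.6) = 0.63 to √(1 + 4) = 2.24. Fasting error therefore does not determine the error of the change.

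**5. Units.** Time to peak is in minutes and the slopes are RER per unit time, while fasting RER has no units. A ratio of their SDs to the fasting RER SD has no meaning. For RER change the units agree, but by step 4 the error term is the wrong one.

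**The case against.** The case on the other side is substantial.

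- *Aim 2 is a secondary, developmental aim of a pilot sized on its award, and measurement in a person is not a phrase in the hypothesis.* This limits how much can be demanded. But flexibility is treated as a property of people in section 3.1, and section 5.2 lists indices computed per person, so asking how well they are measured is fair.
- *Section 5.2 goes beyond a comparison of means.* This stands: the indices are named. The gap is that no analysis or criterion is attached to them.
- *A reader might infer that almost any data would confirm the hypothesis.* The documents do not support this. The indices could visibly fail, for example through no identifiable peak or no return to baseline within 5 hours. What is missing is a stated threshold.
- *A reader might infer that the study would yield no error estimate at all.* Also unsupported. A mixed model with both meals per person gives a residual variance, usable for planning a later crossover of the same contrast.
- *A reader might infer that the existing duplicates give the measurement error of flexibility for free.* They do not. They give fasting error only, as steps 4 and 5 show.
- *A reader might take section 3.1 to admit that flex-chamber repeatability is unknown.* Its statement that "the reproducibility of this method across metabolic chambers and clinical populations has not yet been determined" concerns a published large-chamber method across chambers and populations. It is context and does not address within-person repeatability in this chamber.
- *The two fasting cart measurements in Behavior Sessions 2 and 4 look like further replicates.* They use a different device, follow a 4-hour fast without diet control, and say nothing about the flex chamber.

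**Conclusion.** The point holds in a limited form. The stated Aim 2 model compares meals, and its significance carries no information about whether flexibility can be measured in an individual. The person-level indices have no repeatability analysis or criterion, and the matched chamber fasting duplicates have no planned reliability use.

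Those duplicates would give a fasting within-person SD with 95% limits of about 0.74 to 1.55 times the estimate, and a CI of 0.51 to 0.93 around an ICC of 0.8. These intervals are wide, but they describe the baseline component of the RER-change and slope indices. They do not establish the reproducibility of any meal response, which this design cannot estimate.

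The precision figures assume 15 people with both sessions and approximately normal errors. The contrast calculation assumes a two-sided 0.05 test and, for the main illustration, a paired difference of 1.5 SD. That reliability does not enter the test holds at any effect size.

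**What to change.** In section 5.2:

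1. Report the within-person SD, ICC and limits of agreement, with 95% CIs, for fasting RER and fasting energy expenditure from the two chamber baselines. Label them as the error of the baseline component of the RER-change and slope indices only. Leave the cart baselines out of this estimate.
2. Report the between-person SD of each listed index descriptively, without dividing it by the fasting error.
3. Recompute each index on the first 3 and first 4 hours after the meal and compare with 5 hours, as an exploratory check of the measurement window.
4. State that a significant meal contrast will not be taken as evidence that flexibility is determined in individuals, and that reproducibility of the meal response cannot be estimated because each meal is given once.

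Reconcile section 1.0 with sections 8.1 and 14.4 on who enters the chamber, because this sets n for every estimate above.

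The cost is SAP wording and a little analysis of data already collected, with no added visits or procedures. The downside is that only fasting error is estimated, with wide intervals.

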3.0 Background

3.1 Summarize the relevant prior research on this topic and gaps in current knowledge within the field of study:

There is conflicting evidence as to whether people with obesity find foods more reinforcing. People with obesity exhibit a greater motivation to consume palatable foods that does not habituate over time compared to healthy weight individuals (Saelens and Epstein 1996; Epstein et al. 2007; Temple et al. 2009); however, they do not report liking food more (Wall et al. 2020). Obesity is also associated with decreased sensitivity to post-ingestive signals (Beutler et al. 2020), possibly due to dietary history and exposure (Small and [name] 2019). Further, there is evidence for impaired reinforcement learning and habituation in studies from both humans with obesity and animals (Kroemer and Small 2016; Coppin et al. 2014; Reichelt, Morris, and Westbrook 2014; Johnson and Kenny 2010). Additionally, many hormones that are altered in states of obesity and metabolic dysfunction, such as insulin, influence food reinforcement. For example, a recent study in humans revealed central insulin signaling influences striatal dopamine tone (Kullmann et al. 2021). However, there is no experimental evidence in humans that post-ingestive learning is altered in states of obesity. The experiments in this proposal aim to fill that gap.

The normal process of energy metabolism involves a dynamic and coordinated switch between primarily fat and carbohydrate as oxidative fuel substrates, depending upon nutritional or physiological condition. This process of adjusting substrate oxidation to match substrate availability and energy demand is termed "metabolic flexibility" (Kelley and Mandarino 1990). Metabolic inflexibility, on the other hand, is caused by nutrient overload in the mitochondria and results in altered nutrient partitioning in which a consistent mix of oxidative substrates, regardless of nutritional or physiological

PROTOCOL (STUDY) TITLE AND NUMBER

circumstances, is utilized (Muoio 2014). Metabolic inflexibility has been identified in obesity (GM et al. 2012; Hulver et al. 2003), type 2 diabetes (Kelley and Mandarino 1990), insulin resistance (Kelley et al. 1999; van der Kolk et al. 2016), and other conditions characterized by dysregulated energy homeostasis. Metabolic inflexibility is putatively a key influence in the pathogenesis of peripheral insulin resistance, as biomarkers of altered fat oxidation have been observed prior to the development of insulin resistance (Jans et al. 2011; Heilbronn et al. 2007). If flavor nutrient conditioning is dependent upon some mechanism involved in the pathway of nutrient sensing, transport, and utilization, altered nutrient partitioning due to metabolic inflexibility may provide insight into the relationship between post-ingestive metabolic signals and food reward in obesity and metabolic disease.

Indirect calorimetry is a powerful tool for determining energy expenditure and macronutrient oxidation in response to a mixed-macronutrient diet or meal. In other words, it allows for a versatility in measurement of metabolic flexibility to both fat and carbohydrate in a physiologically relevant manner. Indeed, a new method for assessing metabolic flexibility to a high-carbohydrate or high-fat meal using indirect calorimetry in a large, whole-room metabolic chamber has recently been published (McDougal et al. 2020); however, the reproducibility of this method across metabolic chambers and clinical populations has not yet been determined. Furthermore, this methodology is designed around use of a 27 m³ chamber, which requires a relatively long duration of measurement for an appropriate temporal resolution of measured O₂ and CO₂ concentrations to determine energy expenditure and macronutrient oxidation (Chen et al. 2018). The Fralin Biomedical Research Institute houses two state-of-the-art metabolic chambers. The smaller of the two chambers, approximately 4.6 cubic meters, allows for more rapid and accurate measurement of O₂ and CO₂ compared to large chambers and is specifically designed for conducting dynamic metabolic studies over shorter measurement durations. This smaller “flex” chamber is one of only a few in the world, and as such, no methodologies to assess metabolic flexibility specifically in the “flex” chamber have been developed. Thus, we are poised to take advantage of novel technology to lead the development of a new method to assess a key component of metabolic health.

3.2 Describe any relevant preliminary data:

This is a new project without preliminary data collected.

3.3 Based on the existing literature, provide the scientific or scholarly rationale for and significance of your research and how will it add to existing knowledge:

PROTOCOL (STUDY) TITLE AND NUMBER

Although substantial advances in obesity treatment have been made in recent decades, obesity remains a public health epidemic. This may in part be due to the fact that although current treatments are effective in improving metabolic health and reducing body weight in the short term, strategies that promote long-term maintenance of metabolic health and reduced body-weight remain elusive. Obesity is therefore a chronic disease that requires lifelong attention. From a public health perspective, developing long-term effective treatments is an essential medical research goal. The gut-brain axis has long been recognized as an important regulator of metabolism and energy homeostasis; however, only recently have advances in research tools allowed for a better understanding of the complex mechanistic integration of gut and brain signals. The fidelity of the gut-brain axis presents a novel and potentially powerful therapeutic target for obesity and metabolic diseases. In this proof-of concept pilot, we propose to probe the gut-brain axis as a target for obesity intervention by testing the fidelity of the gut-brain axis 1) across a range of body mass index (BMI) and 2) in states of altered metabolic health (independent of BMI). The data from this proposal will provide evidence for the gut-brain axis as a therapeutic target in obesity treatment and allow the development of state-of-the-art tools to measure metabolic health at Virginia Tech, essential steps towards applying for federal funding.

